4.6 FOLLOW-UP ASSESSMENTS

4.6.1 Ongoing Imaging Assessments for Disease Recurrence

Patients assigned to atezolizumab (Arm A) who complete the treatment phase (16 cycles or 1 year, whichever occurs first) will discontinue treatment with atezolizumab. Patients without recurrence will continue to undergo imaging assessments for recurrence (disease recurrence follow-up phase) every 12 weeks for 2 years (i.e., during Years 2 and 3); every 24 weeks for another 2 years (i.e., during Years 4 and 5); and at Year 6, until DFS event, loss to follow-up, withdrawal of consent, or study termination by the Sponsor, whichever occurs first. *After the primary analysis, patients in Years 2–3 of the study may be assessed for tumor recurrence every 24 weeks.* Investigators may perform additional scans or more frequent assessments if clinically indicated. Patients who discontinue study drug for reasons other than disease recurrence (e.g., toxicity) should continue to undergo scheduled imaging assessments for recurrence until DFS event, loss to follow-up, consent withdrawal, or study termination by the Sponsor whichever occurs first.

Patients assigned to observation (Arm B) who complete the initial observation period (16 cycles or 1 year, whichever occurs first) will also continue to undergo imaging assessments as specified above for Arm A patients. Investigators may perform additional scans or more frequent assessments if clinically indicated.

4.6.2 Adverse Events

All adverse events, regardless of attribution, will be recorded until 30 days after the last dose of study drug (for patients in Arm A) or 30 days after the last day of the observation period (for patients in Arm B), or the initiation of another anticancer therapy, whichever occurs first. Serious adverse events (see Section 5.2.2) and protocol defined adverse events of special interest (see Section 5.2.3) will be recorded until 90 days after the last dose of study drug or until the initiation of another anti-cancer therapy, whichever occurs first (for patients in Arm A).

After the treatment/observation discontinuation visit, adverse events should be followed as outlined in Section 5.6.

4.6.3 Anti-Therapeutic Antibody and Pharmacokinetic Assessments

For patients assigned to atezolizumab only, a post-treatment ATA and PK sample should be collected 120 days (± 30 days) after the last dose of study drug unless the patient withdraws consent or the study closes.

See the schedules of assessments provided in [Appendix 1](#) and [Appendix 2](#) for specified follow-up assessments.

4.6.4 Survival and Subsequent Anti-Cancer Therapy

Survival follow-up information will be collected via telephone calls, patient medical records, and/or clinic visits approximately every 3 months *from the completion or discontinuation of the treatment/observation period* until death, loss to follow-up, or study termination by the Sponsor. All patients will be followed for survival and all new anti-cancer therapy information unless the patient requests to be withdrawn from follow-up (this request must be documented in the source documents and signed by the investigator) or the study is terminated by the Sponsor. If the patient withdraws from study, the study staff may use a public information source (e.g., county records) to obtain information about survival status only.

Patients who have completed the treatment or observation phase and continue in disease recurrence follow-up should have survival follow-up *in parallel* approximately every 3 months. All patients must still be followed for new anti-cancer therapy.

Before considering a patient lost to follow-up, at least three different documented attempts to contact them should be made. If local regulations permit, the attempts should include but not be limited to:

- A written contact (e.g., letter by certified mail or email with read receipt)
- Contact with the patient's primary care physician (where the patient has consented to this type of contact)

4.7 PATIENT, TREATMENT, STUDY, AND SITE DISCONTINUATION

4.7.1 Patient Discontinuation

Patients have the right to voluntarily withdraw from the study at any time for any reason. In addition, the investigator has the right to withdraw a patient from the study at any time. Reasons for withdrawal from the study may include, but are not limited to, the following:

- Patient withdrawal of consent at any time
- Any medical condition that the investigator or Sponsor determines may jeopardize the patient's safety if he or she continues in the study
- Investigator or Sponsor determines it is in the best interest of the patient
- Patient non-compliance

Every effort should be made to obtain information on patients who withdraw from the study. Patients who withdraw their consent to be followed for the primary study endpoint (DFS) will be asked to continue follow-up for OS. The primary reason for withdrawal from the study should be documented on the appropriate eCRF. However, patients will not be followed for any reason after consent has been withdrawn. Patients who withdraw from the study will not be replaced.

4.7.2 Discontinuation from Study Drug

Patients must discontinue study treatment if they experience any of the following:

- Pregnancy
- Disease recurrence (local recurrence, urinary tract recurrence, or distant metastasis of UC), as determined by the investigator, documented by radiographic evidence. For patients with UTUC, disease recurrence determined by visual appearance of UC in bladder is acceptable with histopathologic confirmation. For UTUC patients with bladder recurrence of PUNLMP or low-grade pTa, continuation of study treatment is allowed after local resection.

The primary reason for study treatment discontinuation should be documented on the appropriate eCRF. Patients who discontinue study treatment prematurely will not be replaced.

4.7.3 Study and Site Discontinuation

The Sponsor has the right to terminate this study at any time. Reasons for terminating the study may include, but are not limited to, the following:

- The incidence or severity of adverse events in this or other studies indicates a potential health hazard to patients.
- Patient enrollment is unsatisfactory.

The Sponsor will notify the investigator if the Sponsor decides to discontinue the study.

The Sponsor has the right to close a site at any time. Reasons for closing a site may include, but are not limited to, the following:

- Excessively slow recruitment
- Poor protocol adherence
- Inaccurate or incomplete data recording
- Non-compliance with the International Conference on Harmonisation (ICH) guideline for Good Clinical Practice
- No study activity (i.e., all patients have completed and all obligations have been fulfilled)

5. ASSESSMENT OF SAFETY

Atezolizumab is approved for the treatment of urothelial carcinoma, non-small cell lung cancer, small-cell lung cancer, and triple-negative breast cancer. Safety studies are currently ongoing and the entire safety profile is not known at this time. The following information is based on results from nonclinical and clinical studies and published data on similar molecules.

5.1 SAFETY PLAN

Measures will be taken to ensure the safety of patients participating in this trial, including the use of stringent inclusion and exclusion criteria (see Sections 4.1.1 and 4.1.2) and close monitoring (as indicated below and in Section 4.5). An iDMC has also been incorporated into the trial design to periodically review aggregate safety data (see the iDMC Charter for a detailed monitoring plan).

Administration of atezolizumab will be performed in a setting with emergency medical facilities and staff who are trained to monitor for and respond to medical emergencies. All adverse events and serious adverse events will be recorded during the trial. Serious adverse events and adverse events of special interest will be recorded until 90 days after the last dose of study drug or until the initiation of another anti-cancer therapy (whichever occurs first) and all other adverse events will be recorded until 30 days after the last dose of study drug or until the initiation of another anti-cancer therapy, whichever occurs first. After this period, investigators should report any serious adverse events that are believed to be related to prior treatment with study drug. The potential safety issues anticipated in this trial, as well as measures intended to avoid or minimize such toxicities, are outlined in the following sections and management of atezolizumab-specific adverse events are outlined in [Appendix 9](#).

5.1.1 Risks Associated with Atezolizumab

Atezolizumab has been associated with risks such as the following: IRRs and immune-mediated hepatitis, pneumonitis, colitis, pancreatitis, diabetes mellitus, hypothyroidism, hyperthyroidism, adrenal insufficiency, hypophysitis, Guillain-Barré syndrome, myasthenic syndrome or myasthenia gravis, meningoencephalitis, myocarditis, nephritis, and myositis. Immune-mediated reactions may involve any organ system and may lead to hemophagocytic lymphohistiocytosis and macrophage activation syndrome (considered to be potential risks for atezolizumab). Refer to [Appendix 9](#) of the protocol and Section 6 of the Atezolizumab Investigator's Brochure for a detailed description of anticipated safety risks for atezolizumab (see [Appendix 6](#) for precautions for anaphylaxis).

5.1.2 General Plan to Manage Safety Concerns

5.1.2.1 Eligibility Criteria

Eligibility criteria were selected to guard the safety of patients in this trial. Results from the nonclinical toxicology studies with atezolizumab, as well as the nonclinical/clinical data from other PD-L1/PD-1 inhibitors, were taken into account. Specifically, patients at risk for study-emergent autoimmune conditions or with a prior diagnosis of autoimmune disease, patients with evidence of acute infections, and patients who have received a live, attenuated viral vaccine within 4 weeks of randomization are excluded from the study (see Section 4.1.2 for additional details).

5.1.2.2 Monitoring

Safety will be evaluated in this study through the monitoring of all serious and non-serious adverse events defined and graded according to NCI CTCAE v4.0. Patients will be assessed for safety (including laboratory values) according to the schedule in [Appendix 1](#). Laboratory values must be reviewed prior to each infusion.

General safety assessments will include serial interval histories, physical examinations, and specific laboratory studies, including serum chemistries and blood counts (see [Appendix 1](#) and [Appendix 2](#) for the list and timing of study assessments).

During the study, patients will be closely monitored for the development of any adverse events, including signs or symptoms of autoimmune conditions and infection.

All serious adverse events (see Section [5.2.2](#)) and protocol-defined events of special interest (see Section [5.2.3](#)) will be reported in an expedited fashion (see Section [5.4.2](#)). In addition, the iDMC will review safety data as described in Section [3.1.1](#).

Patients who experience a serious adverse event or protocol defined events of special interest will be followed for safety for 90 days following their last dose of study drug or until they receive another anti-cancer therapy, whichever comes first. Patients who experience all other adverse events will be followed for safety for 30 days following their last dose of study drug or until they receive another anti-cancer therapy, whichever comes first.

For patients in Arm A who have an ongoing study drug-related adverse event upon treatment completion or at discontinuation from study treatment will be followed until the event has resolved to baseline grade, the event is assessed by the investigator as stable, new anti-cancer treatment is initiated, the patient is lost to follow-up, the patient withdraws consent, or it has been determined that study treatment or participation is not the cause of the adverse event.

5.1.3 Atezolizumab Dose Modification

There will be no dose reduction for atezolizumab in this study. Patients may temporarily suspend study treatment for up to 42 days beyond the last dose if they experience adverse events that require a dose to be held. If atezolizumab is held because of adverse events for >42 days beyond the last dose, then the patient will be discontinued from atezolizumab and will be followed for safety and efficacy.

If, in the judgment of the investigator, the patient is likely to derive clinical benefit from atezolizumab after a hold of >42 days, study drug may be restarted with the approval of the Medical Monitor.

If a patient must be tapered off steroids used to treat adverse events, atezolizumab may be held for additional time beyond 42 days from the last dose until steroids are

discontinued or reduced to prednisone dose (or dose equivalent) ≤ 10 mg/day. The acceptable length of interruption will depend on an agreement between the investigator and the Medical Monitor.

Dose interruptions for reason(s) other than toxicity, such as surgical procedures, may be allowed with Medical Monitor approval. The acceptable length of interruption will depend on agreement between the investigator and the Medical Monitor.

5.1.4 Management of Atezolizumab-Specific Adverse Events

Toxicities associated or possibly associated with atezolizumab treatment should be managed according to standard medical practice. Additional tests, such as autoimmune serology or biopsies, may be used to determine a possible immunogenic etiology.

Although most immune-mediated adverse events observed with immunomodulatory agents have been mild and self-limiting, such events should be recognized early and treated promptly to avoid potential major complications. Discontinuation of atezolizumab may not have an immediate therapeutic effect and in severe cases, immune-mediated toxicities may require acute management with topical corticosteroids, systemic corticosteroids, or other immunosuppressive agents.

The primary approach to Grade 1–2 immune-mediated adverse events is supportive and symptomatic care with continued treatment with atezolizumab; for higher grade immune-mediated adverse events, atezolizumab should be held and oral/parenteral steroids administered. Recurrent Grade 2 immune-mediated adverse events may also mandate withholding atezolizumab or the use of steroids. Consideration for benefit–risk balance should be made by the investigator, with consideration of the totality of information as it pertains to the nature of the toxicity and the degree of clinical benefit a given patient may be experiencing prior to further administration of atezolizumab. Atezolizumab should be permanently discontinued in patients with life-threatening immune-mediated adverse events.

See [Appendix 9](#) for details on management of gastrointestinal, dermatologic, endocrine, pulmonary toxicity, hepatotoxicity, pancreatic, eye, neurologic, or renal toxicity, and other immune-mediated adverse events. See Section [5.3.5.2](#) for guidelines for the recording and reporting of infusion-related reactions (see [Appendix 6](#) for precautions for anaphylaxis).

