5.3.3 Assessment of Severity of Adverse Events

The adverse event severity grading scale for the NCI CTCAE v4.0 will be used for assessing adverse event severity. Table 8 will be used for assessing the severity for adverse events that are not specifically listed in the NCI CTCAE.

Table 8 Adverse Event Severity Grading Scale

Grade	Severity
1	Mild; asymptomatic or mild symptoms; clinical or diagnostic observations only; or intervention not indicated
2	Moderate; minimal, local, or non-invasive intervention indicated; or limiting age-appropriate instrumental activities of daily living ^a
3	Severe or medically significant, but not immediately life threatening; hospitalization or prolongation of hospitalization indicated; disabling; or limiting self-care activities of daily living ^{b, c}
4	Life-threatening consequences or urgent intervention indicated ^d
5	Death related to adverse event ^d

NCI CTCAE = National Cancer Institute Common Terminology Criteria for Adverse Events.

Note: On the basis of the NCI CTCAE (Version 4.0), which can be found at:

http://evs.nci.nih.gov/ftp1/CTCAE/CTCAE_4.03_2010-06-14_QuickReference_8.5x11.pdf

- ^a Instrumental activities of daily living refer to preparing meals, shopping for groceries or clothes, using the telephone, managing money, etc.
- ^b Examples of self-care activities of daily living include bathing, dressing and undressing, feeding one's self, using the toilet, and taking medications, as performed by patients who are not bedridden.
- ^c If an event is assessed as a "significant medical event," it must be reported as a serious adverse event (see Section 5.4.2 for reporting instructions), per the definition of serious adverse event in Section 5.2.2.
- ^d Grade 5 events must be reported as serious adverse events (see Section 5.4.2 for reporting instructions), per the definition of serious adverse event in Section 5.2.2.

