Risks Associated with Atezolizumab and Guidelines for Management of Adverse Events Associated with Atezolizumab (cont.)

Table 1 Management Guidelines for Pulmonary Events, Including Pneumonitis

Event	Management
Pulmonary event, Grade 1	
 • Continue atezolizumab and monitor closely. • Re-evaluate on serial imaging. • Consider patient referral to pulmonary specialist.
Pulmonary event, Grade 2	
 • Withhold atezolizumab for up to 12 weeks after event onset. ^a • Refer patient to pulmonary and infectious disease specialists and consider bronchoscopy or BAL. • Initiate treatment with 1–2 mg/kg/day oral prednisone or equivalent. • If event resolves to Grade 1 or better, resume atezolizumab. ^b • If event does not resolve to Grade 1 or better while withholding atezolizumab, permanently discontinue atezolizumab and contact Medical Monitor. ^c • For recurrent events, treat as a Grade 3 or 4 event.
Pulmonary event, Grade 3 or 4	
 • Permanently discontinue atezolizumab and contact Medical Monitor. ^c • Bronchoscopy or BAL is recommended. • Initiate treatment with 1–2 mg/kg/day oral prednisone or equivalent. • If event does not improve within 48 hours after initiating corticosteroids, consider adding an immunosuppressive agent. • If event resolves to Grade 1 or better, taper corticosteroids over ≥ 1 month.

BAL=bronchoscopic alveolar lavage.

^a Atezolizumab may be withheld for a longer period of time (i.e., > 12 weeks after event onset) to allow for corticosteroids (if initiated) to be reduced to ≤ 10 mg/day oral prednisone or equivalent. The acceptable length of the extended period of time must be agreed upon by the investigator and the Medical Monitor.

^b If corticosteroids have been initiated, they must be tapered over ≥ 1 month to ≤ 10 mg/day oral prednisone or equivalent before atezolizumab can be resumed.

^c Resumption of atezolizumab may be considered in patients who are deriving benefit and have fully recovered from the immune-mediated event. Patients can be re-challenged with atezolizumab only after approval has been documented by both the investigator (or an appropriate delegate) and the Medical Monitor.

Appendix 9

Risks Associated with Atezolizumab and Guidelines for Management of Adverse Events Associated with Atezolizumab (cont.)

HEPATIC EVENTS

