Symptomatic adrenal insufficiency, Grade 2–4	
 • Withhold atezolizumab for up to 12 weeks after event onset.^a • Refer patient to endocrinologist. • Perform appropriate imaging. • Initiate treatment with 1–2 mg/kg/day IV methylprednisolone or equivalent and convert to 1–2 mg/kg/day oral prednisone or equivalent upon improvement. • If event resolves to Grade 1 or better and patient is stable on replacement therapy, resume atezolizumab.^b • If event does not resolve to Grade 1 or better or patient is not stable on replacement therapy while withholding atezolizumab, permanently discontinue atezolizumab and contact Medical Monitor.^c
Hyperglycemia, Grade 1 or 2	
 • Continue atezolizumab. • Initiate treatment with insulin if needed. • Monitor for glucose control.
Hyperglycemia, Grade 3 or 4	
 • Withhold atezolizumab. • Initiate treatment with insulin. • Monitor for glucose control. • Resume atezolizumab when symptoms resolve and glucose levels are stable.

MRI=magnetic resonance imaging; TSH=thyroid-stimulating hormone.

^a Atezolizumab may be withheld for a longer period of time (i.e., > 12 weeks after event onset) to allow for corticosteroids (if initiated) to be reduced to ≤ 10 mg/day oral prednisone or equivalent. The acceptable length of the extended period of time must be agreed upon by the investigator and the Medical Monitor.

^b If corticosteroids have been initiated, they must be tapered over ≥ 1 month to ≤ 10 mg/day oral prednisone or equivalent before atezolizumab can be resumed.

^c Resumption of atezolizumab may be considered in patients who are deriving benefit and have fully recovered from the immune-mediated event. Patients can be re-challenged with atezolizumab only after approval has been documented by both the investigator (or an appropriate delegate) and the Medical Monitor.

Appendix 9

Risks Associated with Atezolizumab and Guidelines for Management of Adverse Events Associated with Atezolizumab (cont.)

Table 4 Management Guidelines for Endocrine Events (cont.)

Event	Management

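### Section 5.1.4 makes continued atezolizumab the primary approach at Grade 2, Appendix 9 withholds it at a first Grade 2 event for 11 event types, and neither text is said to govern

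*Protocol*

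**What the plan says.** The third paragraph of Protocol Section 5.1.4 sets out a general scheme by severity.

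- Grade 1–2: "The primary approach to Grade 1–2 immune-mediated adverse events is supportive and symptomatic care with continued treatment with atezolizumab".
- Named exception: "Recurrent Grade 2 immune-mediated adverse events may also mandate withholding atezolizumab or the use of steroids".
- Above Grade 2: "for higher grade immune-mediated adverse events, atezolizumab should be held and oral/parenteral steroids administered".
- Life-threatening: "Atezolizumab should be permanently discontinued in patients with life-threatening immune-mediated adverse events".

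The paragraph also asks the investigator to weigh benefit and risk, taking account of the nature of the toxicity. The next paragraph refers the reader to Appendix 9 for the listed organ systems and for other immune-mediated events.

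Appendix 9 gives actions by event type and grade. For a Grade 2 pulmonary event (Appendix 9, Table 1) the dosing instruction is "Withhold atezolizumab for up to 12 weeks after event onset". For Grade 3 or 4 in the same table it is to "permanently discontinue atezolizumab and contact Medical Monitor". The symptomatic adrenal insufficiency row (Appendix 9, Table 4) covers Grades 2 to 4 together and says: "If event resolves to Grade 1 or better and patient is stable on replacement therapy, resume atezolizumab".

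The cross-references do not rank the two texts. Section 4.3.2.1 lists Sections 5.1.3 and 5.1.4 and Appendix 9 together as the guidelines for interruption, discontinuation and event management. Section 1.2.2.2 points to Section 5.1.4 for immune-mediated events, and Section 5.1 points to Appendix 9.

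**The concern.** An investigator with a patient who has a first Grade 2 pneumonitis, myocarditis or nephritis finds continued dosing as the primary approach in the body of the protocol and withholding in the appendix. For several of these events the texts also differ on systemic corticosteroids, which Section 4.4.2 says may attenuate the benefit of atezolizumab.

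Three things are at stake.

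- **Patient safety:** the texts differ on whether to dose during an active immune-mediated event, in a trial planned for approximately 200 sites (Section 9.4).
- **Reported tolerability:** adverse events leading to withdrawal or interruption of study drug are planned summaries (Protocol Section 6.5; SAP Section 4.5.2). Their frequency could depend partly on which text a site follows.
- **Deviations:** a site that follows one text departs from the other, so compliance cannot be judged consistently.

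**Working it through.** No formula applies. The check is a row-by-row reading of Appendix 9 against Section 5.1.4. It covers all 16 graded event types. It leaves out infusion-related reactions and cytokine-release syndrome (own grading system), and the thyroid and HLH/MAS rows (not graded). In the table, stop means permanent discontinuation.

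| Event type (Appendix 9 table) | Grade 2 | Grade 3 | Grade 4 |
|---|---|---|---|
| Pulmonary (1) | withhold | stop | stop |
| Hepatic (2) | withhold if > 5 days; otherwise closer liver-test monitoring | stop | stop |
| Diarrhea/colitis (3) | withhold | withhold | stop |
| Symptomatic adrenal insufficiency (4) | withhold | withhold | withhold, may resume |
| Hyperglycemia (4) | continue | withhold | withhold, may resume |
| Hypophysitis (4) | withhold | withhold | stop |
| Ocular (5) | withhold | stop | stop |
| Myocarditis (6) | withhold | stop | stop |
| Amylase/lipase elevation (8) | continue | withhold | withhold, may resume |
| Pancreatitis (8) | withhold | withhold | stop |
| Dermatologic (9) | continue | withhold | stop |
| Neuropathy (10) | withhold | stop | stop |
| Myasthenia gravis/Guillain-Barré (10) | stop | stop | stop |
| Meningoencephalitis (11) | stop | stop | stop |
| Renal (12) | withhold | stop | stop |
| Myositis (13) | withhold | withhold | stop |

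**Grade 2 (Section 5.1.4: continue).** 11 rows withhold and 2 stop, so 11 + 2 = 13 of 16 differ and 3 agree. The hepatic row is split: events of 5 days or less carry no withholding and so agree with Section 5.1.4. None of the 11 rows requires recurrence before withholding, so the recurrence exception in Section 5.1.4 does not account for them. Six of the 11 (pulmonary, hepatic > 5 days, adrenal insufficiency, hypophysitis, pancreatitis, renal) also start systemic corticosteroids at that point, where Section 5.1.4 describes supportive care.

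**Grade 1.** The two rows that stop at any grade differ from Section 5.1.4 here as well.

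**Grade 3 (Section 5.1.4: hold and give steroids).** Six organ-specific rows stop (pulmonary, hepatic, ocular, myocarditis, neuropathy, renal), as do the two any-grade neurologic rows: 6 + 2 = 8 of 16. The other 8 withhold, as Section 5.1.4 does.

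**Grade 4 (Section 5.1.4: stop if life-threatening).** 13 of 16 rows stop. Three withhold and allow resumption: adrenal insufficiency, hyperglycemia and amylase/lipase elevation.

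**The case against.** The strongest reply is that Section 5.1.4 is a summary. It speaks of a primary approach, asks for benefit-risk judgment and sends the reader to Appendix 9, and organ-specific tables are naturally read as governing a general sentence. Section 5.1 supports this by pointing to Appendix 9 for management. The qualifiers are real, and Section 5.1.4 should not be read as a flat rule. But a summary whose Grade 2 statement differs from 13 of 16 rows does not summarize them. It names only recurrence as an exception, and Sections 1.2.2.2 and 4.3.2.1 direct readers to Section 5.1.4 as guidance in its own right.

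A reader might infer that the two texts give opposite instructions at Grades 3 and 4 too. The documents do not support that.

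- **Grade 3:** both texts stop dosing, and five of the six organ-specific rows that discontinue also start systemic corticosteroids (neuropathy defers to institutional guidelines). The difference is whether the stop is provisional or permanent. Even a permanent stop is open to re-challenge after full recovery, with documented approval, under the introduction to Appendix 9. Half the rows agree with Section 5.1.4.
- **Grade 4:** Section 5.1.4 says life-threatening, not Grade 4. Protocol Table 8, which grades events not listed in NCI CTCAE, defines Grade 4 as "Life-threatening consequences or urgent intervention indicated", so the two are not equivalent. A Grade 4 laboratory elevation need not be life-threatening, and the hyperglycemia rows are not labelled immune-mediated. That leaves symptomatic adrenal insufficiency as the one clear example.

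It also stands that the consequence is not demonstrated. Efficacy is analyzed by assigned arm (Protocol Section 6.4; SAP Section 4.4), and interruptions and withdrawals enter only descriptive safety summaries. Nothing in the documents shows that a site followed Section 5.1.4 over the tables.

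**Conclusion.** The point holds as an internal inconsistency centered on Grade 2: 13 of 16 graded event types differ from the approach in Section 5.1.4, with shorter hepatic events as a partial exception, and no text is given precedence. The Grade 3 mismatch is secondary: hold versus permanent discontinuation in six organ-specific rows. At Grade 4 it rests on adrenal insufficiency alone, assuming a Grade 4 case is judged life-threatening.

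The documents do not support a stronger conclusion that patients were mismanaged or that the primary comparison is affected. Urgency depends on how much dosing remains. Treatment lasts at most one year, and the primary analysis comes at least 12 months after the last enrollment (Section 6.1.2), so little scheduled dosing would be left by then. The correction should be made, but it is not a reason to question the design.

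**What to change.** Reconcile the third paragraph of Protocol Section 5.1.4 with Appendix 9, and state which text governs where they differ. The Grade 2 sentence is the priority. The higher-grade and life-threatening sentences should be checked in the same edit against the six Grade 3 rows and the adrenal insufficiency row. Sections 1.2.2.2, 4.3.2.1 and 5.1 should then point to the governing text. The clinical content of each rule is for the sponsor's clinical team; this review takes no view on which action is right.

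The cost is one paragraph in a protocol amendment with its cross-references, the ethics committee and regulatory approvals described in Section 9.6, and a letter to sites. No analysis, sample size or data collection changes.
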